**Low-Cost, Virtual Reality System to Increase Access to Exposure Therapy for
Anxiety and Obsessive Compulsive Disorders**

NCT 03636022

Date: 5/15/2024

Study Protocol

Children with childhood anxiety disorders (CADs) or obsessive compulsive disorder (OCD) and a parent will be recruited to test the VR system with a randomized controlled mixed methods study. Participants will be identified by through a Pediatric Anxiety Disorders Clinic using purposive sampling methods. All patients complete a standardized diagnostic assessment (including the MINI KIDS and Spence Child Anxiety Scales, Parent & Child report and begin treatment with psychoeducation on parent-coached exposure therapy for anxiety and OCD, create a treatment plan (i.e., fear hierarchy), and proceed to treatment sessions focused on completion of exposures. Participants will be recruited after their initial assessment and will begin the study in the early stages of treatment after completing psychoeducation and treatment planning.

Participants will be randomly assigned to home exposure practice with or without the VR system, i.e., intervention or control, respectively. All participants in the study will participate in an introductory session in which they complete two exposures related to content from their fear ladder, one with the VR system and an analogous imaginal exposure. Each family will receive instructions for how to use the exposure tracking form to record exposures during home practice. Participants will then be assigned one week of daily exposure homework for both the intervention and control conditions. Patients randomized to the intervention condition will take home the VR system for homework completion and participants assigned to control will be instructed to complete imaginal exposures. One week after the introductory session, all participants will return for a session in which they complete both types of exposure. They will also be assigned third generalization exposure, i.e., an exposure related to the baseline exposure that is higher on the fear ladder, to complete at their next anxiety clinic treatment session. Subjective Units of Distress (SUDS) ratings for each type of exposure will be recorded on paper with the exposure tracking form. During the follow up session, an independent interviewer will observe participants' engagement during exposures and will interview participants and their parents about their experience with both types of exposure.

Study Population

Potential participants will be ages 7 to 17 years old; have a diagnosis of CAD (i.e., generalized anxiety disorder, separation anxiety disorder, specific phobia, panic disorder with or without agoraphobia) or OCD; and have at least one fear fitting exposures covered by the VR system. Qualifying diagnoses will be based on standardized assessments in the Clinic (MiniKIDS). Potential participants will be excluded if they have a high likelihood of being lost to follow-up or contact; are unable to provide good data; have significant comorbidity that would interfere with participation (e.g., uncontrolled oppositional defiant disorder) or are at heightened risk of self-harm (e.g., presence of active suicidal ideation reported on clinical interview or endorsement on a self-report measures, such as the PHQ-9M). Research assistants (RA) will approach eligible patients and describe the study. The RA will then obtain written informed consent from the parents and written informed assent from the child. Every effort will be made to enroll subjects in proportion to the gender and racial/ethnic demographics of the treatment population.

Study Protocol

Following recruitment and consent and assent, participants will be randomly assigned to the intervention or control condition. Then, participants will complete a baseline study session with study staff at the Clinic. At this session, the staff member will follow a standardized protocol to instruct all participants and their parents on how to use the exposure tracking form to electronically record exposure practice. Because all study participants will have started treatment in the Clinic, including orientation to parent-coached exposure, participating families

will be familiar with parent-coached exposure procedures. Standard Clinic treatment includes parent-coached exposure in and between sessions. For the study baseline session, a Clinic psychologist/therapist will follow the standardized protocol to guide all participants through planning two exposures related to content from their personalized fear ladder, one with the VR system and an analogous imaginal exposure (order randomized). Parent-child dyads will complete these exposures in session with study staff present (in most cases, the research coordinator). During each exposure, the participant will record his or her anxiety using a 0 to 10 SUDS rating scale, the standard procedure during clinical care and between-session exposures. For the VR exposure, the staff member will ask the participant to follow instructions presented by the VR program. The conventional exposure will follow common clinical practice for imaginal exposures; specifically, the participant will write a story about their fears coming true and then read the story aloud. In each condition, the staff member will encourage the participant to repeat the exposure until anxiety ratings are reduced by 50%. Based on clinical experience and confirmed during earlier research, it is anticipated that participants' anxiety will be manageable throughout the exposure and will have habituated by the end of the exercise. Each of the study sessions will be approximately 90 minutes. In the unlikely event of difficulties during a study session, and in accordance with the safety monitoring plan, the lead psychologists will be available to evaluate the participant, address emotional distress, and arrange appropriate care. Throughout the course of the study (i.e., between study sessions), participants will have access to the lead psychologists as well as the supports of typical clinical care including the treating therapist, or a covering clinician through the Clinic Division of Child Psychiatry and Psychology will be available for research participants 24 hours a day, 7 days a week. The exposure activity and SUD ratings for each exposure will be recorded on paper with the exposure tracking form. Each participant will be asked to wear a sensor on their wrist during the in-office exposures. These sensors are similar to an activity tracker. The sensors will measure real-time physiological data (i.e. heart rate, acceleration, body temperature, etc). This information will allow the study team to note changes with the patient as they participate in the exposures. It will also provide valuable data that can be analyzed at the end of the study. These sensors do not collect any patient health information. The sensors will either Empatica E4 but in the event the study team cannot get the Empatica 4, they will use the Elite HRB CorSense.

Participants will then be assigned one week of daily exposure homework with or without VR, depending on condition, using a paper exposure tracking form to record each exposure and SUDS. Patients randomized to intervention will take home the VR system for homework completion, and participants assigned to control will not take the VR system home and will be instructed to complete imaginal exposures. Participants will be asked to record each exposure, even if it is not related to the fear addressed with the baseline exposures, in order to capture all exposures completed during the homework period.

One week after the baseline session, all participants will return for a follow up session in which they complete both types of exposure (order randomized) and will receive an assignment to complete in their next Clinic therapy appointment a third generalization exposure, i.e., an exposure related to the baseline exposure that is higher on the fear ladder for the targeted fear, following procedures analogous to the baseline session. During the follow up session, staff from Clinic Health Care Policy & Research ("the interviewer") experienced in qualitative data analysis and not involved with the patients' medical care or development of the prototype system will observe, record, and code participants' engagement in the exposures and will interview participants about their experience with both types of exposure and then will ask for observations and opinions from the parent. A psychologist from the Clinic Health Care Policy & Research will work with the two lead child psychologists to identify questions and topics for a

semi-structured interview guide. The guide will be pilot-tested to ensure that questions and follow-up probes are easily comprehended and delivered in a sensitive manner. The semi-structured guide will follow guidelines for minimizing bias and increasing the reliability and validity of interview data[64,65]. All interviews will be audio-recorded.

During the participants' next therapy session, they will complete the assigned generalization exposure. SUDS ratings will be recorded for that exposure using the paper exposure tracking form, and participants will wear a sensor to obtain biometrics during the exposure.

Thus, study participation will include the two study sessions, completion and recording of exposures for one week between study sessions, and completion of a study-assigned exposure in a subsequent Clinic therapy session. Participation consent and assent will include agreement for clinically gathered assessments to be used for the study (i.e., initial structured interview, symptom rating scales completed at initial evaluation and clinic treatment follow up, number of treatment sessions attended, length of treatment). Study participants will continue with any treatment as usual during study participation.

Participant Recruitment & Participation Flow

Initial Clinic visit	Baseline Study Visit	1 week out-of-session exposure	Follow up Study Visit	Next Therapy Session	End of treatment assessments
Complete diagnostic interview & questionnaires as part of usual clinic procedures; If the patient meets study criteria, the Clinic psychologist/therapist will invite the patient and parent to participate	Informed Consent/Assent. 2 Baseline exposures. Participant will wear a sensor to obtain biometrics and SUDS ratings will be collected.	Participants will be instructed to practice daily either the VR exposure or imaginal exposure, depending on study condition, and to record exposures using the exposure tracking form	Repeat 2 baseline exposures. Participant will wear a sensor to obtain biometrics and SUDS ratings will be collected. Participants assigned generalization exposure to complete in next therapy session Qualitative interview and observation. Complete the Spence Child Anxiety Scales and the Child Sheehan Disability Scale. Participant will wear a sensor to obtain biometrics.	Participant will complete the assigned generalization exposure during therapy session following the Follow up Study Visit Participant will wear a sensor to obtain biometrics and SUDS ratings will be collected.	Participants complete questionnaires as part of usual clinic procedures. Study staff records data related to treatment length and # treatment sessions. Post-Treatment from Clinic
Participants continue with any treatments as usual, including treatment through Clinic					

Statistical Analysis Plan

Analysis Plan

The primary outcomes of the study are: (1) difference in maximum SUDS ratings during time 1 exposures between VR and conventional, 2) difference in number of exposures completed to assigned item (as well as overall) between conditions; 3) difference in maximum SUDS rating in cross over exposure between conditions during time 2; and 4) difference in maximum SUDS rating in generalization exposure between conditions during time 2. We will also conduct exploratory analyses to see if decrease in anxiety symptoms, as measured by the Spence Child Anxiety Scales, Child and Parent reports, and improvement in functional impairment, as measured by the Child Sheehan Disability Scale, differ between groups.

Quantitative analysis: Descriptive and inferential statistics will be used, including means, standard deviations, medians, ranges, frequency distributions, t-tests, and Analyses of Variance (ANOVAs). Specifically: a) differences in maximum SUDS ratings during VR and traditional exposures during time 1 session will be examined using a paired-samples t-tests, b) change over time in the peak anxiety ratings for each modality (VR vs. imaginal) will be examined using Repeated Measures ANOVAs with VR status as the between subjects variable and change in anxiety rating (T1 to T2 difference in maximal SUDS for VR vs. T1 to T2 difference in maximal SUDS for imaginal) being the within subjects variable, c) differences between homework exposure conditions, on maximal anxiety in the generalization exposure at time 2 controlling for time 1 maximal SUDS averaged across exposure conditions will be examined using Analyses of Covariance (ANCOVA) with homework condition as the between subjects variable and number of completed exposures and average maximum anxiety across the two time 1 exposures as the covariates; and d) ANCOVA will be used to compare average number of homework exposures completed to target item (as well as overall exposures) during the study time frame between the conditions (i.e. VR vs. imaginal) controlling for patient characteristics (age, sex, diagnoses). Exploratory analyses will compare change in anxiety symptoms from time 1 to time 2 between conditions, controlling for patient characteristics, and examining number of completed exposures as a mediator of change.

Qualitative analysis: We will conduct semi-structured interviews during the second study session with both the child and parent. These interviews will collect data on the participant's experiences, opinions, perceived benefits and barriers, and engagement with the system. An inductive coding approach will be used to condense these data and to identify themes. The Division of Health Care Policy & Research employs approximately 386 allied health and 62 doctoral level staff including survey research, qualitative research, statistical support, and chart review personnel as well as a dedicated publication specialist on staff. HCPR has created a core of behavioral scientists with expertise in qualitative research. They psychologist from HCPR has experience in qualitative research in the evaluation of mental health interventions. Analysts with experience in qualitative data analysis will code interviews using methods of content analysis, i.e., systematic process of sorting and coding information based on themes. QSR's NVivo 2010 qualitative data software analysis program will be used to facilitate data coding and sorting.

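### Analysis c) adjusts primary outcome 4 for the number of completed exposures, itself primary outcome 2, so it does not estimate the effect of assignment; separately, the four primaries have no alpha or claim rule

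*Combined protocol and SAP*

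**What the plan says.** The Analysis Plan gives a numbered list of four primary outcomes, with no ranking:

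1. The list opens with a comparison of modalities within each child: "The primary outcomes of the study are: (1) difference in maximum SUDS ratings during time 1 exposures between VR and conventional"
2. Next comes the amount of home practice, in two versions: "difference in number of exposures completed to assigned item (as well as overall) between conditions"
3. Then follows a contrast at the follow-up session: "difference in maximum SUDS rating in cross over exposure between conditions during time 2"
4. Last is the harder, related exposure: "difference in maximum SUDS rating in generalization exposure between conditions during time 2"

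Under Quantitative analysis, outcome 1 has its own within-child test, a): "differences in maximum SUDS ratings during VR and traditional exposures during time 1 session will be examined using a paired-samples t-tests". Outcome 2 is served by d), an ANCOVA on both counts. Outcome 4 is served by c), an ANCOVA with homework condition as the factor and "number of completed exposures and average maximum anxiety across the two time 1 exposures as the covariates". The sentence introducing c) mentions control only for the time 1 average; the count enters when the covariates are listed.

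That leaves b) for outcome 3. It is a repeated-measures ANOVA whose within-child term is "T1 to T2 difference in maximal SUDS for VR vs. T1 to T2 difference in maximal SUDS for imaginal".

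The exploratory analyses compare change in anxiety symptoms between conditions, "examining number of completed exposures as a mediator of change".

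The documents give no significance level, testing order, multiplicity adjustment, rule for what counts as success, sample size or power target.

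**The concern.** Outcome 4 asks whether children assigned to VR homework differ from those assigned to imaginal homework when they meet a harder, related exposure. If VR works partly because children practise more, that extra practice is part of the effect of assignment. A model that holds practice fixed removes that part and answers a different question. It also conditions on something the children do after the conditions diverge, so randomisation no longer protects the comparison. The trial could report no effect on generalization where there is one, or the reverse.

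The second matter is what may be claimed. With four primaries and no rule, the plan leaves open whether one significant result is enough or whether each outcome is reported only as its own question. That choice affects the error rate and should be made before the data are seen.

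**Working it through.** The documents give no figure to reproduce on these points. The check has three parts.

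**A. Outcome 4 and the count**

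*Timing (Study Protocol section).* Random assignment comes first, then the baseline session with both exposures for everyone, one week of homework by condition, the follow-up session, and the generalization exposure at the next therapy session. The count therefore arises after the conditions diverge and before outcome 4 is measured. The time 1 average also follows assignment, but it comes before any homework and from the same two exposures in both arms, so it carries no homework effect.

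*Algebra.* Let Z be arm, M the count, Y the generalization maximum SUDS and X the time 1 average.

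- M = m0 + a·Z + error
- Y = y0 + d·Z + b·M + g·X + error
- Total effect of assignment = d + a·b
- Arm coefficient in c) = d, at best

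The two agree only if a·b = 0, that is, if homework condition does not change the count or the count does not affect SUDS. Whether a differs from zero is what outcome 2 tests, so c) cannot assume it away.

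*Size.* In a simulated check with an assumed effect acting only through the count (d = 0), the adjusted arm effect was about 0 against a true total of −0.32, on that check's own scale.

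*Bias.* If something unmeasured, such as motivation, drives both practice and SUDS, children with equal counts in the two arms will tend to differ in it. The coefficient in c) is then biased even for d. The documents do not determine the direction.

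**B. Error rate if any one result may be claimed**

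Assumed, because the plan states neither: each test at two-sided 0.05, and any one significant between-condition result may be claimed. For k tests the risk is 1 − 0.95^k under independence, and at most 0.05·k whatever the correlation.

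| Between-condition tests | Independence | Bound |
|---|---|---|
| Outcomes 2–4 as written, both counts (k = 4) | 1 − 0.95^4 = 18.5% | 20% |
| Outcomes 2–4, one count only (k = 3) | 1 − 0.95^3 = 14.3% | 15% |

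Positive correlation lowers these figures. With all tests equally correlated at 0.3, 0.5 and 0.8, four tests give 17.4%, 15.6% and 11.4%, and three give 13.6%, 12.5% and 9.8%. With the two counts correlated 0.8 and all other pairs 0.3, four tests give 16.0%. All the correlations are assumed.

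**C. Outcome 3**

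The term *cross over exposure* is not defined, and b) does not say which of its effects answers outcome 3. Every child does both modalities at follow-up, so one natural reading is the modality not practised at home. On that reading, imaginal SUDS in the VR arm are compared with VR SUDS in controls, and arm is confounded with modality.

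A time 1 covariate does not remove this. Assume a 0.5 SD modality difference at both times, a time 1 to time 2 correlation of 0.5 and no homework effect. The adjusted difference is then 0.5 − 0.5 × 0.5 = 0.25 SD, not zero. In simulation, outcome 3 alone was rejected at 0.0167 in 6.4% of trials with 40 children and about 9% with 60 (sample sizes assumed). Holm across outcomes 2–4 gave a family-wise rate of 4.3–4.9% when outcome 3 was simulated without a modality difference and outcome 4 was not adjusted for the count. That result does not carry over to the confounded contrast.

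**The case against.** **Adjustment for practice may be intended.** The plan lists the count openly, and a comparison at equal practice is a legitimate question. That stands as a reason to keep the model as a secondary analysis. It does not make it the analysis of outcome 4, which is worded as a plain difference between conditions.

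**The plan's own mediator language.** A reader might infer that the plan itself declares the count a mediator of generalization SUDS. It does not: it names that role only in the exploratory analysis of symptom change. The point rests on the timing of the count and on its being outcome 2; the mediator wording is context. Nor does it follow that c) must come out null. The check above shows what happens if the effect runs wholly through practice, which is assumed.

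**Distinct questions need no correction.** Outcomes 1, 2 and 4 have their own analyses and address different constructs in a mixed-methods study with no single stated efficacy claim. If each is reported only as its own question, per-test error applies and there is no family-wise inflation. If all had to succeed, there would be none either. This objection largely stands. A reader might infer that the trial runs an 18.5% false-positive risk, but the documents do not support that as a fact, because they contain no rule that one success is enough. The firm gap is that the plan states neither an alpha nor which reading applies.

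**Conclusion.** The main point holds as written. Analysis c) does not estimate the total effect of assignment on outcome 4. The discrepancy is a·b, the effect of condition on practice times the effect of practice on SUDS, plus any bias from common causes. The documents do not allow either to be sized for this trial.

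The second point holds conditionally. The missing alpha and claim rule are certain. The risk of 18.5% (bound 20%) for the four tests the wording implies, or 14.3% (bound 15%) with one count, depends on 0.05 per test, on any one result being claimable and, for the first figure of each pair, on independence. A reader who counts one test per outcome will arrive at the 15% bound, but outcome 2 and analysis d) both name two counts.

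Outcome 3 cannot be tested cleanly until its contrast is defined, and no multiplicity procedure repairs a contrast that confounds arm with modality.

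**What to change.** - **Outcome 4.** Make the primary model arm plus the time 1 average maximum SUDS. Report the count-adjusted model as secondary. This costs almost nothing: any precision the count adds relates to a different quantity.
- **Outcome 2.** Make the assigned-item count the test and the overall count secondary.
- **Outcome 3.** Define *cross over exposure*. Pre-specify one contrast that compares the arms on the same modality, or averages both modalities, adjusted for the matching time 1 value.
- **Claims.** State a two-sided alpha of 0.05. Either name one primary between-condition test or apply Holm across outcomes 2–4. Report outcome 1 as a separate within-child question.

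No data collection changes, but this is more than rewording: it alters the model for outcome 4, specifies a new contrast for outcome 3 and demotes the overall count.

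Holm costs power. The first step needs p ≤ 0.05/3 = 0.0167, a critical value of 2.394. A test with 80% power at 0.05 (assumed; none is stated) has an expected statistic of 1.960 + 0.842 = 2.802, so its power at that step is Φ(2.802 − 2.394) = 0.658, about 66%. If all three effects are real and independent, average power per test is about 75%. Naming one primary test avoids this loss but makes the other two secondary.

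### Primary outcome 3 rests on an undefined time 2 cross over exposure, and the only analysis left for it tests change in both modalities without saying which term decides

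*Combined protocol and SAP*

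**What the plan says.** **The outcome.** The Statistical Analysis Plan (Analysis Plan) gives four primary outcomes. The third is the "difference in maximum SUDS rating in cross over exposure between conditions during time 2". This is the only place where a cross over exposure is mentioned.

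**The exposures at time 2.** The follow-up visit in the Participant Recruitment & Participation Flow table reads "Repeat 2 baseline exposures. Participant will wear a sensor to obtain biometrics and SUDS ratings will be collected". The Study Protocol text agrees that all participants do both types. Neither exposure is labelled as the cross over one.

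**The homework.** Children are told to "practice daily either the VR exposure or imaginal exposure, depending on study condition". The Study Protocol adds that "participants assigned to control will not take the VR system home and will be instructed to complete imaginal exposures". The modality left unpractised therefore differs between arms.

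**The analysis.** Item b of the quantitative analysis specifies "Repeated Measures ANOVAs with VR status as the between subjects variable". Its within-subjects variable is "T1 to T2 difference in maximal SUDS for VR vs. T1 to T2 difference in maximal SUDS for imaginal". No main effect, interaction or simple contrast is named as the deciding test.

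**The concern.** A primary outcome needs a defined measurement and one test that settles it. Outcome 3 has neither. Each child has two time 2 maximum SUDS ratings that could be the endpoint. The outcome is worded as a time 2 level, while the remaining analysis uses change. That analysis also has two terms that involve the homework condition, and they can give opposite answers on the same data.

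With nothing fixed in advance, the deciding test of a primary outcome could be picked after the results are seen. That raises the false-positive rate. It also leaves open whether the outcome asks if VR homework is better overall, or if each kind of homework helps mainly in the modality practised.

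**Working it through.** **Step 1. Match analyses to outcomes.**

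| Primary outcome | Matching analysis |
|---|---|
| 1: "difference in maximum SUDS ratings during time 1 exposures between VR and conventional" | a, paired t-test at time 1 |
| 2: number of exposures completed | d, ANCOVA on homework counts |
| 3: time 2 maximum SUDS, cross over exposure | none by wording; b by elimination |
| 4: time 2 maximum SUDS, generalization exposure | c, ANCOVA |

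Assigning b to outcome 3 is an inference. So is reading its between-subjects factor as homework condition.

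**Step 2. Inputs.** The documents give the 0 to 10 SUDS scale, but no sample size, SD, correlation or significance level. All of the following is assumed: SD 2.5, four ratings per child (two modalities, two times) equally correlated at r, two-sided 0.05, 30 per arm unless stated, benefits of 1 point, normal ratings.

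**Step 3. What each term of b tests.** Let V and I be a child's VR and imaginal change scores.

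- Homework main effect: arm difference in (V + I)/2. Variance per child SD²(1 − r) = 6.25 × 0.5 = 3.125 at r = 0.5. SE = √(2 × 3.125/30) = 0.456.
- Homework-by-modality interaction: arm difference in V − I. Variance per child 4·SD²(1 − r) = 12.5. SE = √(2 × 12.5/30) = 0.913.

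*Pattern A: VR homework lowers time 2 SUDS by 1 point more in both modalities.* Homework effect 1, noncentrality 1/0.456 = 2.19, power 0.577 by noncentral t (simulated 0.574). Interaction 0, rejects in 5%.

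*Pattern B: each arm gains 1 point only in the modality it practised.* Homework effect 0, rejects in 5%. Interaction 2 in absolute value, noncentrality 2/0.913 = 2.19, power 0.577 (simulated 0.577).

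**Step 4. Type I error if either term may decide.** For two independent tests, 1 − 0.95² = 0.0975. Simulation (20,000 trials per setting) gave 0.094 to 0.100 for 20 to 50 per arm and r = 0.3 to 0.7.

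**Step 5. Precision of b against T1 adjustment, averaged over modalities.** The correlation between a child's mean T1 and mean T2 rating is R = 2r/(1 + r). The change score has variance SD²(1 − r) and the ANCOVA has SD²(1 + r)/2 × (1 − R²). The ratio, ANCOVA to change score, is (1 + R)/2.

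| r | R | Variance ratio | Power for 1 point, change score | Power, ANCOVA |
|---|---|---|---|---|
| 0.3 | 0.46 | 0.73 | 0.445 | 0.567 |
| 0.5 | 0.67 | 0.83 | 0.577 | 0.655 |
| 0.7 | 0.82 | 0.91 | 0.794 | 0.829 |

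If same-modality ratings correlate at 0.7 and all others at 0.4, R = 0.55/0.70 = 0.79 and the ratio is 0.89, with power about 0.80 against 0.84. The gain is then smaller.

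**Step 6. Why the definition must come before the test.** Suppose VR homework carries over fully to imaginal exposure and imaginal homework does not carry over to VR (1-point benefits, r = 0.5). The arm difference is −1.00 within VR, 0.00 within imaginal and −0.50 averaged. ANCOVA power is about 42% within VR and 21% averaged.

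**The case against.** **The meaning can be guessed.** Given the homework design, the likeliest reading is the modality not practised at home. That is fair, but it is never stated. It also leaves open whether level or change is meant, and which term decides.

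**Analysis b is a legitimate method.** This stands. Its homework main effect is not biased by a VR-versus-imaginal difference that is stable over time. It is only less precise, and how much less depends on assumed correlations. Preferring ANCOVA is an efficiency argument; the defect is the missing specification.

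**A reader might infer that outcome 3 is confounded with modality**, because the unpractised modality is imaginal in the VR arm and VR in controls. With homework effect G and modality effect M, that raw time 2 contrast is (μ + G/2 − M/2) − (μ − G/2 + M/2) = G − M, and M is what outcome 1 examines. The documents do not support calling this a flaw of the plan. No listed analysis makes that raw comparison, and a stable M cancels in the change scores that b uses. It is a caution for whoever writes the definition.

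**A reader might also count b's modality main effect as a third route to significance.** Outcome 3 is worded as a difference between conditions, so on the reading that conditions means homework arms, that term cannot decide it. Only two terms are in play.

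**Conclusion.** The point holds as a failure of specification that should be fixed. Primary outcome 3 names an undefined exposure, its wording (time 2 level) does not match the remaining analysis (change in both modalities), and that analysis names no deciding term. These three facts come from the text and need no assumed numbers.

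The consequence is about 10% type I error if either between-condition term may be chosen, a figure that hardly moves with sample size or correlation over the ranges tried. Rejection rates are about 57% against 5%, or 5% against 58%, depending on which term is read and on the pattern of benefit. Those rates rest on the assumed SD, correlation and sample size, and on normal ratings that ignore the bounds of the scale. The validity of b's homework effect also takes T1 ratings as unaffected by arm.

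The documents do not show that b is invalid or that the plan commits to a confounded contrast.

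**What to change.** In the Analysis Plan, the sponsor should state which time 2 exposure is the cross over exposure and name one matching test. This should be dated before time 2 data are compared by arm; otherwise it should be labelled post hoc.

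- **Form of the test.** Compare homework conditions within the same modality: ANCOVA of time 2 maximum SUDS on homework condition and same-modality T1 maximum SUDS. Item c already adjusts in a similar way ("average maximum anxiety across the two time 1 exposures as the covariates"). Unlike c, leave out number of completed exposures: it arises after homework starts and is itself primary outcome 2.
- **If the unpractised modality is meant.** Use the within-imaginal contrast (carry-over of VR homework) and the within-VR contrast (carry-over of imaginal homework) as a Holm-adjusted pair.
- **If both repeated exposures are meant.** Use the ANCOVA of each child's mean time 2 maximum on homework condition and mean T1 maximum.
- **Sensitivity.** Keep b's change-score analysis in this role.
- **Caution.** Do not compare raw imaginal SUDS in one arm with raw VR SUDS in the other.

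**Cost.** One degree of freedom for the covariate, and some power lost to Holm if the pair is used. No new data are needed, since both modalities are rated at both sessions. One limit remains: with no arm without homework, no between-arm contrast can separate equal full carry-over in both arms from no benefit in either.
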